6.4 STUDY INTERVENTION/EXPERIMENTAL MANIPULATION ADHERENCE

The interventionist will record attendance during each of the group sessions.

6.5 CONCOMITANT THERAPY

N/A

6.5.1 RESCUE THERAPY

N/A

7 STUDY INTERVENTION/EXPERIMENTAL MANIPULATION DISCONTINUATION AND PARTICIPANT DISCONTINUATION/WITHDRAWAL

7.1 DISCONTINUATION OF STUDY INTERVENTION/EXPERIMENTAL MANIPULATION

When a subject discontinues from study intervention but not from the study, remaining study procedures will be completed as indicated by the study protocol. If a clinically significant finding is identified after enrollment, the investigator or qualified designee will determine if any change in participant management is needed. Any new clinically relevant finding will be reported as an adverse event (AE).

The data to be collected at the time of study intervention discontinuation will include the following:

- The reason(s) for discontinuing the participant from the intervention, and methods for determining the need to discontinue
- The participant will be included in all future scheduled assessments, even though not participating in the intervention.

7.2 PARTICIPANT DISCONTINUATION/WITHDRAWAL FROM THE STUDY

Participants are free to withdraw from participation in the study at any time upon request.

An investigator may discontinue a participant from the study for the following reasons:

- Lost-to-follow up; unable to contact subject (see **Section 7.3, Lost to Follow-Up**)
- Any event or medical condition or situation occurs such that continued collection of follow-up study data would not be in the best interest of the participant or might require an additional treatment that would confound the interpretation of the study
- The participant meets an exclusion criterion (either newly developed or not previously recognized) that precludes further study participation

The reason for participant discontinuation or withdrawal from the study will be recorded in the study record. Subjects who sign the informed consent form, and are randomized and receive the study intervention, and subsequently withdraw, or are discontinued from the study, will not be replaced.

7.3 LOST TO FOLLOW-UP

Participants will be considered lost to follow-up if they cannot be contacted for the 24-week study assessment within the assessment window. To minimize missing data, staff will attempt to follow up with all participants randomized into the study regardless of their level of participation in the intervention or completion of the 12-week assessment (i.e., those who fail to complete the 12-week assessment will be contacted to complete the 24-week assessment). Importantly, no subject is considered lost to follow up at any earlier point in the study, even if they miss other assessments. Retention efforts should continue throughout the entire duration of the study

8 STUDY ASSESSMENTS AND PROCEDURES

8.1 ENDPOINT AND OTHER NON-SAFETY ASSESSMENTS

Assessments will occur at baseline and 3 and 6 months post-randomization. Assessments will occur in three parts: in-person assessment, online questionnaires, and (optional) semi-structured interviews.

In person assessment visits

Participants will come to the study site for in-person assessments. Assessments will be conducted by study staff in private rooms. Measures include weight (measured in duplicate in street clothes with shoes removed and heavy objects removed from pockets), height (baseline only), and a physical activity interview. The physical activity interview is based on the Paffenbarger physical activity measure^{3 4} but will be conducted as an interview to allow follow up questions to correctly categorize physical activities reported.

Online questionnaires

Participants will be provided with a personalized link to an online survey where they will complete all of the self-report measures for each time point.

Satisfaction with program (3 and 6 months): Satisfaction with the program questions are modeled after other weight control program evaluation questions^{51 52} and ask the participant to consider their satisfaction and their satisfaction given the effort they put into the program. The participants will also rate the likelihood they will continue to engage in the behaviors encouraged by the program. Participants in the BELT intervention will also be asked to evaluate specific program components.

Eating behaviors: Vegetable intake will be assessed using the all-day Screener developed for the NCI Eating at America's Table Study (EATS). This 10-item questionnaire asks participants the frequency and amount of vegetables they consumed over the past month. Frequency of fast food consumption will be assessed using the questions from the CARDIA study Participants will be asked to report how frequently they eat fast food in a week and whether the meals are for breakfast, lunch, dinner or snacks. Beverage consumption will be assessed using the Family Life, Activity, Sun, Health and Eating (FLASHE) beverage screener. This screener assesses the frequency of drinking seven common beverages.

Weight control behaviors: a 45-item questionnaire will assess how frequently participants engaged in specific weight control strategies⁵³ . These strategies include approaches to weight control encouraged by the program and strategies not included to assess the intervention effects.

Healthcare climate questionnaire: The Healthcare climate questionnaire is an established scale⁵⁴ .that asses the study team provided the level of autonomous support.

Substance use: Tobacco use will be asked via four yes or no questions taken from the Population Assessment of Tobacco and Health Study (PATH). This assesses current and lifetime smoking, use of electronic, smokeless, and other forms of tobacco. Alcohol consumption will be assessed using two questions including the number of days in the last month alcohol was consumed and the number of drinks consumed each time. Alcohol misuse will be assessed during screening only and will use the alcohol related items from the Alcohol, Smoking and Substance Involvement Screening Test (ASSIST) measure.

Weight history questions: The survey will ask participants to report their highest, lowest, and ideal weight; the weight they would like to lose during the program, frequency of self-weighing, their number of prior weight loss attempts, their reasons for losing weight, and approaches to weight loss they have used before (e.g., commercial program).

Demographic characteristics: Demographic characteristics as age, marital status, household members, income, education, occupational status, race, and ethnicity will be collected. Self-reported history of medical conditions will also be collected.

Optional Semi-structured interviews

Up to five participants in each treatment arm will be asked to complete a brief semi-structured interview about their experiences in the weight loss program they have received following the in-person assessment visits at 3 and 6 months. These interviews will focus on their motivation to join the program, their satisfaction and evaluation of the program components, and their suggestions for future changes to the program.

8.2 SAFETY ASSESSMENTS

Data on adverse events will be collected at each assessment point after baseline and documented as they arise. Unanticipated problems that are also deemed to be serious adverse events will be reported to the IRB immediately, and not later than 24 hours from the time the investigator becomes aware of the event. Any other unanticipated problem or adverse event will be reported to the IRB within 1 week.

8.3 ADVERSE EVENTS AND SERIOUS ADVERSE EVENTS

8.3.1 DEFINITION OF ADVERSE EVENTS

The DHHS Office of Human Research Protections (OHRP) defines the following types of events in research involving human subjects: Any untoward or unfavorable medical occurrence in a human

subject, including any abnormal sign (for example, abnormal physical exam or laboratory finding), symptom, or disease, temporally associated with the subject's participation in the research, whether or not considered related to the subject's participation in the research.

8.3.2 DEFINITION OF SERIOUS ADVERSE EVENTS

An adverse event that results in death; is life-threatening; results in inpatient hospitalization or prolongation of existing hospitalization; results in a persistent or significant disability/incapacity; results in a congenital anomaly/birth defect; or may jeopardize the subject's health and may require medical or surgical intervention.

8.3.3 CLASSIFICATION OF AN ADVERSE EVENT

8.3.3.1 SEVERITY OF EVENT

The following guidelines will be used to describe the severity of an adverse event:

Mild: Events require minimal or no treatment and do not interfere with the participant's daily activities.

Moderate: Events result in a low level of inconvenience or concern with the therapeutic measures.

Moderate events may cause some interference with functioning.

Severe: Events interrupt a participant's usual daily activity and may require systemic drug therapy or other treatment. Severe events are usually potentially life-threatening or incapacitating. Of note, the term "severe" does not necessarily equate to "serious".

8.3.3.2 RELATIONSHIP TO STUDY INTERVENTION/EXPERIMENTAL MANIPULATION

All adverse events (AEs) will have their relationship to study procedures, including the intervention, assessed by an appropriately-trained clinician based on temporal relationship and his/her clinical judgment. The degree of certainty about causality will be graded using the categories below.

- **Definitely Related:** There is clear evidence to suggest a causal relationship, and other possible contributing factors can be ruled out. The clinical event, including an abnormal laboratory test result, occurs in a plausible time relationship to study procedures administration and cannot be explained by concurrent disease or other drugs or chemicals. The response to withdrawal of the study procedures should be clinically plausible. The event must be pharmacologically or phenomenologically definitive.
- **Probably Related:** There is evidence to suggest a causal relationship, and the influence of other factors is unlikely. The clinical event, including an abnormal laboratory test result, occurs within a reasonable time after administration of the study procedures, is unlikely to be attributed to concurrent disease or other drugs or chemicals, and follows a clinically reasonable response on withdrawal.
- **Potentially Related:** There is some evidence to suggest a causal relationship (e.g., the event occurred within a reasonable time after administration of study procedures). However, other factors may have contributed to the event (e.g., the participant's clinical condition, other concomitant events). Although an AE may rate only as "possibly related" soon after discovery, it can be flagged as requiring more information and later be upgraded to "probably related" or "definitely related", as appropriate.

- **Unlikely to be related:** A clinical event, including an abnormal laboratory test result, whose temporal relationship to study procedures administration makes a causal relationship improbable (e.g., the event did not occur within a reasonable time after administration of the study procedures) and in which other drugs or chemicals or underlying disease provides plausible explanations (e.g., the participant's clinical condition, other concomitant treatments).
- **Not Related:** The AE is completely independent of study procedures administration, and/or evidence exists that the event is definitely related to another etiology. There must be an alternative, definitive etiology documented by the clinician.

8.3.3.3 EXPECTEDNESS

A clinician with appropriate expertise in will be responsible for determining whether an adverse event (AE) is expected or unexpected. An AE will be considered unexpected if the nature, severity, or frequency of the event is not consistent with the risk information previously described for the study procedures.

8.3.4 TIME PERIOD AND FREQUENCY FOR EVENT ASSESSMENT AND FOLLOW-UP

The occurrence of an adverse event (AE) or serious adverse event (SAE) may come to the attention of study personnel during study visits and treatment sessions of a study participant.

All AEs will be captured on the appropriate case report form (CRF). Information to be collected includes event description, time of onset, clinician assessment of severity, relationship to study procedures (assessed only by those with the training and authority to make a diagnosis), and time of resolution/stabilization of the event. All AEs occurring while on study will be documented appropriately regardless of relationship. All AEs will be followed to adequate resolution.

Any medical or psychiatric condition that is present at the time that the participant is screened will be considered as baseline and not reported as an AE. However, if the study participant's condition deteriorates at any time during the study, it will be recorded as an AE.

Changes in the severity of an AE will be documented to allow an assessment of the duration of the event at each level of severity to be performed. Documentation of onset and duration of each episode will be maintained for AEs characterized as intermittent.

Study staff will record events with start dates occurring any time after informed consent is obtained until 7 (for non-serious AEs) or 30 days (for SAEs) after the last day of study participation. At each study visit, the investigator will inquire about the occurrence of AE/SAEs since the last visit. Events will be followed for outcome information until resolution or stabilization.

8.3.5 ADVERSE EVENT REPORTING

In consultation with the PI, a trained member of the study team will be responsible for conducting an evaluation of an adverse event and shall report the results of such evaluation to the NIH and the reviewing Institutional Review Board (IRB) as soon as possible, but in no event later than 10 working days after the investigator first learns of the event.

8.3.6 SERIOUS ADVERSE EVENT REPORTING

In consultation with the PI, a trained member of the study team will be responsible for conducting an evaluation of an adverse event and shall report the results of such evaluation to the NIH and the reviewing Institutional Review Board (IRB) as soon as possible, but in no event later than 10 working days after the investigator first learns of the event.

8.3.7 REPORTING EVENTS TO PARTICIPANTS

N/A

8.3.8 EVENTS OF SPECIAL INTEREST

N/A

8.3.9 REPORTING OF PREGNANCY

N/A

8.4 UNANTICIPATED PROBLEMS

8.4.1 DEFINITION OF UNANTICIPATED PROBLEMS

This protocol uses the definition of Unanticipated Problems as defined by the Office for Human Research Protections (OHRP). OHRP considers unanticipated problems involving risks to participants or others to include, in general, any incident, experience, or outcome that meets all of the following criteria:

- Unexpected in terms of nature, severity, or frequency given (a) the research procedures that are described in the protocol-related documents, such as the Institutional Review Board (IRB)-approved research protocol and informed consent document; and (b) the characteristics of the participant population being studied;
- Related or possibly related to participation in the research ("possibly related" means there is a reasonable possibility that the incident, experience, or outcome may have been caused by the procedures involved in the research); and
- Suggests that the research places participants or others at a greater risk of harm (including physical, psychological, economic, or social harm) than was previously known or recognized.

8.4.2 UNANTICIPATED PROBLEMS REPORTING

The investigator will report unanticipated problems (UPs) to the reviewing Institutional Review Board (IRB). The UP report will include the following information:

- Protocol identifying information: protocol title and number, PI's name, and the IRB project number
- A detailed description of the event, incident, experience, or outcome

- An explanation of the basis for determining that the event, incident, experience, or outcome represents an UP
- A description of any changes to the protocol or other corrective actions that have been taken or are proposed in response to the UP

To satisfy the requirement for prompt reporting, UPs will be reported using the following timeline:

- UPs that are serious adverse events (SAEs) will be reported to the IRB and to the funding agency within 24 hours of the investigator becoming aware of the event
- Any other UP will be reported to the IRB and to the DCC/study sponsor/funding agency within 7 days of the investigator becoming aware of the problem

8.4.3 REPORTING UNANTICIPATED PROBLEMS TO PARTICIPANTS

N/A

9 STATISTICAL CONSIDERATIONS

9.1 STATISTICAL HYPOTHESES

The primary aims of this study are to examine the acceptability of tailored behavioral weight loss program to a standard program in men working in blue-collar occupations and to compare recruitment approaches that vary on trust-based messaging to recruit men with overweight/obesity who work in blue-collar occupations. There are no formal hypotheses to be tested.

9.2 SAMPLE SIZE DETERMINATION

This is a feasibility study. No formal sample size estimations were conducted. Instead the sample size was selected to produce appropriate size treatment groups ($n = 15$) for two interventions across two cohorts ($N = 60$).

9.3 POPULATIONS FOR ANALYSES

We will use an intention-to-treat analysis population where we will include all participants randomized to the study. Similarly, the population for the recruitment substudy includes the 4000 addressees that sent the postcards minus those addresses who's postcards are returned.

9.4 STATISTICAL ANALYSES

9.4.1 GENERAL APPROACH

General presentation of data will be dependent on the distributions of the final data. The majority of outcomes reported will be descriptive in nature.

9.4.2 ANALYSIS OF THE PRIMARY ENDPOINT(S)

The primary outcome is acceptability of the interventions. These will be presented descriptively and will be reported as continuous data unless data is highly skewed in which case, the proportion of participants that reported that the treatment is acceptable will be reported. We will compare differences in the portion of participants randomized into the study by recruitment message type using chi-square analysis.

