Engaging men from blue-collar industries in weight loss: Study 3- Evaluating the Acceptability of Weight Loss Treatments

Unique Protocol Identification Number: 18013105-IRB01

National Clinical Trial (NCT) Identified Number: NCT05386238

Principal Investigator: [name]

Sponsor: Rush University Medical Center

**Grant Title: Engaging men from blue-collar industries in weight loss: Tailoring
recruitment and treatment approaches**

Grant Number: K01DK119457

Funded by: NIDDKD

Version Number: v.1.000

11 May 2022

Title:

Engaging men from blue-collar industries in weight loss

Grant Number:

K01DK119457

Study Description:

Objectives*:

Primary Objective: Aim 1: Examine the acceptability of tailored behavioral weight loss program and a standard program in men working in blue-collar occupations.

Aim 2: Compare recruitment approaches that vary on trust-based messaging to recruit men with overweight/obesity who work in blue-collar occupations.

Secondary
Objectives:

Determine the feasibility of retaining participants to a randomized trial over six months.

Determine the reach of recruitment messages.

Endpoints*:

Primary Endpoint: Aim 1: Participant reported satisfaction at 3 months.

Aim 2: Proportion of participants who enroll in study by recruitment type.

| | |
|---|---|
| Secondary Endpoints: | Number of visits to recruitment websites by recruitment type. Participant reported satisfaction at 6 months. Percentage of participants who complete a weight assessment at the 6-month assessment timepoint. |
| Study Population: | Men working in blue-collar occupations with overweight or obesity. |
| Phase* or Stage: | Feasibility testing |
| Description of Sites/Facilities | Single site |
| Enrolling Participants: | |
| Description of Study Intervention/Experimental Manipulation: | This protocol is for a randomized pilot study that will test the acceptability of a novel weight loss program and a standard weight loss program in men with overweight or obesity who work in blue-collar occupations. The secondary aim of the study is to test in a randomized comparison the effect of recruitment messages that enhance trust in two ways: researcher trust enhancement (Yes, No) x participant endorsement (Yes, No). |
| Study Duration*: | 18 months |
| Participant Duration: | 6 months |

Table of Contents

| | |
|---|----|
| Statement of Compliance | 5 |
| Investigator's Signature | 5 |
| 1 Protocol Summary | 6 |
| 1.1 Synopsis | 6 |
| 1.2 Schema | 8 |

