3 OBJECTIVES AND ENDPOINTS

| OBJECTIVES | ENDPOINTS | JUSTIFICATION FOR ENDPOINTS |
|--|--|--|
| Primary | | |
| Aim 1: Examine the acceptability of tailored behavioral weight loss program and a standard program in men working in blue-collar occupations. | Participant reported satisfaction with program acceptability at 3 months. | Participant satisfaction is a proxy for program acceptability. |
| Aim 2: Compare recruitment approaches that vary on trust-based messaging to recruit men with overweight/obesity who work in blue-collar occupations. | Proportion of participants who enroll in study by recruitment message type. | The goal of recruitment is enrollment in the study. Using the proportion of participants who received the postcard as the endpoint provides an assessment of the effectiveness of the message. |
| Secondary | | |
| Determine the feasibility of retaining participants to a randomized trial over six months. | Percentage of participants who complete a weight assessment at the 6-month assessment timepoint. | High retention to the study will indicate the study procedures are feasible for a fully powered trial. |
| Determine the reach of recruitment messages. | Number of visits to recruitment websites. | The website is the first indication of participant interest in the study. |
| Determine the acceptability of the intervention. | Participant reported satisfaction with program at 6 months. | |
| Tertiary/Exploratory | | |
| Determine percentage of participants who achieve a clinically significant weight reduction (5% of initial weight). | Weight objectively assessed by study staff at baseline, 3 months, and 6 months. | 5% weight loss is an established indicator of clinically significant weight loss. |
| Evaluate participants perceptions of program components. | Semi-structured interviews. | We will conduct semi-structured interviews with participants to gain a deeper understanding of their perceptions of program components and their experiences in the program. |

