4 STUDY DESIGN

4.1 OVERALL DESIGN

This study is a two-armed randomized controlled trial with assessments at baseline, 3 months after randomization, and 6 months after randomization. The objective is to assess the acceptability of the intervention to participants at 3 months and the feasibility of study procedures at 6 months with retention to the study as the outcome. This is a single site, Stage 1 study.

Participants will be randomly assigned to study groups by a biostatistician who is not involved with the study assessments or interventions using a random number generator. Individuals will be randomly assigned to study conditions in cohorts of approximately 30 individuals. Randomization will be concealed from participants until their first treatment session.

Participants will be randomized to receive either the tailored BELT (Better Energy through Lifestyle for Tradesmen) treatment or a standard weight loss program (Diabetes Prevention Program Group Lifestyle Balance; DPP GLB). The groups will be matched on number of weeks of treatment, mode of delivery, and contact time.

During recruitment for this study, we will conduct a randomized comparison of recruitment messages. This comparison will use a factorial design testing the effects of enhancing trust in the researchers (Trust Messaging: Yes, No) and the effects of a participant endorsement (Endorsement: Yes, No). Names and addresses for individuals from a purchased marketing list will be randomly assigned to be sent a postcard with a recruitment message matching their assigned condition. Recruitment reach will be assessed through website visits and number of participants responding to each message.

This is a feasibility study with no formal hypotheses to be tested.

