4.2 SCIENTIFIC RATIONALE FOR STUDY DESIGN

This study will use a randomized design to test the feasibility of recruiting and retaining men working in blue collar occupations into a study of multiple weight loss programs. This study will use a previously tested, effective, publicly available program as the comparison group ³⁸. The benefits of using the program include that all participants will receive an active intervention and we will have data on men's performance in a standard weight loss program as well as our tailored program at the end of this study. This will be key preliminary data for future grant applications. A potential problem associated with using this control group is that participants may not be interested in a non-tailored program if a tailored program is available. This may decrease both recruitment and retention to the study.

To enhance recruitment for this study and future studies, we will use a randomized, factorial design to test the efficacy of two components of recruitment messaging. By using this factorial design, no participants will be randomized to a true control group: all participants will receive a message we believe may be effective for recruitment of this population.

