5.5 STRATEGIES FOR RECRUITMENT AND RETENTION

Participants will be recruited via the postcards mailed to their homes. They will be directed to a study website where a brief description of the study will be presented. Participants recruited through the four recruitment messages will be sent to separate but identical websites. Participants who are interested will be asked to complete an online screening form. Those who appear initially eligible will be contacted to schedule a time to attend a study orientation. This orientation will allow participants the opportunity to gain information about the study and to experience the web conferencing platform (if they have not used it before). The session will describe the study and will use the motivational interviewing approach described by Kiernan and colleagues ^{44, 45, 46} to enhance engagement and retention to the study. Following this, participants will attend an in-person assessment visit where they will sign consent before completing the physical measures and self-report questionnaires. Participants who complete the baseline visit and measures will be randomized to receive either the tailored intervention or the generic intervention following a 1:1 randomization ratio.

Recruitment will be supplemented by recruitment through flyers, notices on a hospital "on-hold" line, and online recruitment messages as needed. These potential participants will be encouraged to contact the study through the study website and will go through the recruitment process described above.

All recruitment materials and plans will be reviewed and approved by the Rush University Institutional Review Board prior to implementation.

To maximize retention, we will collect multiple methods for contacting participants (e.g., email, telephone) at baseline. Participants will tentatively schedule their follow-up assessment during their initial treatment session, a method we have used in prior studies to increase retention rates. During the intervention, participants have not engaged with treatment for at least one anticipated sessions will be contacted directly by intervention staff to encourage reengagement with the program.

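### The recruitment substudy is a 2x2 factorial meant to test two message components, but section 9.4.2 plans only a chi-square by message type and section 9 has no factor-level analysis

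*Combined protocol and SAP*

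**What the plan says.** Section 4.1 describes the recruitment substudy as a randomised comparison: "This comparison will use a factorial design testing the effects of enhancing trust in the researchers" and, as a second factor, of a participant endorsement, each at levels yes and no. Section 4.2 gives the purpose: "we will use a randomized, factorial design to test the efficacy of two components of recruitment messaging". The synopsis also sets the two factors out as yes/no.

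Section 3 words Aim 2 more loosely ("Compare recruitment approaches that vary on trust-based messaging") and gives its endpoint as "Proportion of participants who enroll in study by recruitment message type". Section 6.1.1 lists four messages: standard, standard plus trust, standard plus endorsement, and both. Section 5.5 keeps them apart operationally: "Participants recruited through the four recruitment messages will be sent to separate but identical websites".

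Section 9.4.2 contains the one planned analysis of enrolment: "We will compare differences in the portion of participants randomized into the study by recruitment message type using chi-square analysis". Section 9.3 defines the substudy population as the 4000 addressees less those whose postcards come back. Section 9.1 says that there are no formal hypotheses, and 9.4.1 says that most outcomes will be reported descriptively.

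**The concern.** The design asks two questions: does trust messaging raise enrolment, and does an endorsement raise it? A chi-square across four messages asks a different one, namely whether the four enrolment proportions differ in any way. Section 9 gives no analysis by factor, no effect estimate and no interval to go with the two effects named in 4.1.

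What is at stake is attribution. Section 4.2 says that the substudy should help recruitment in this and future studies, and for that the investigators need to know which component to carry forward and roughly how much it adds. If the four proportions are published, a reader can work out the factor margins. The choice of contrast would then have been made after seeing the data, and no estimate per component would have been promised.

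**Working it through.** **Inputs from the documents.** 4000 addressees (9.3); four messages (6.1.1); trial target N = 60 (9.2), which reproduces as 15 per group x 2 interventions x 2 cohorts = 60. No power, alpha or sample-size figure is given for the substudy, so there is none to reproduce.

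**Assumptions.** Equal allocation (4000/4 = 1000 per message), no returned postcards, all 60 enrolments through postcards, two-sided 0.05. The overall enrolment proportion is then 60/4000 = 0.015, or 15 expected per message.

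**Four-group test.** Chi-square = sum of (observed - 15)^2 / (1000 x 0.015 x 0.985). Take three tables, in the order standard/trust/endorsement/both: 10/20/10/20, 10/10/20/20 and 10/20/20/10. Every cell is 5 away from 15, so each table gives 4 x 25 / 14.775 = 6.77 on 3 df, p = 0.080. The test cannot tell them apart.

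**Factor margins (2000 addresses per level).** The SE of the log risk ratio is sqrt(1/a - 1/2000 + 1/b - 1/2000).

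- 40 vs 20: ratio 2.0; SE = sqrt(0.025 + 0.050 - 0.001) = 0.272; 95% CI 1.17 to 3.41. Risk difference 1.0 percentage point (0.25 to 1.75).
- 30 vs 30: ratio 1.0; SE = sqrt(0.0667 - 0.001) = 0.256; 95% CI 0.61 to 1.65. Risk difference 0 (-0.75 to 0.75).

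| Table | Trust ratio | Endorsement ratio | Interaction ratio (95% CI) |
|---|---|---|---|
| 10/20/10/20 | 2.0 | 1.0 | 1.00 (0.34 to 2.91) |
| 10/10/20/20 | 1.0 | 2.0 | 1.00 (0.34 to 2.91) |
| 10/20/20/10 | 1.0 | 1.0 | 0.25 (0.09 to 0.73) |

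The interaction ratio is (both/endorsement)/(trust/standard). Its log has SE sqrt(1/10 + 1/20 + 1/10 + 1/20 - 4/1000) = 0.544, so its interval runs about 2.9-fold each way. With equal cells, the Mantel-Haenszel stratified ratios equal the marginal ones.

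**Fewer postcard enrolments.** Section 5.5 allows other channels ("Recruitment will be supplemented by recruitment through flyers"). With the same 2:1 split, the ratio's 95% CI is about 1.04 to 3.85 at 40 postcard enrolments and 0.79 to 5.06 at 20.

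**Contrast left open.** By simulation with no true effect and 15 expected per cell, the 3-df test alone has p < 0.05 in about 5% of trials. At least one of the 3-df test and the two main effects, each at 0.05, does so in about 11%.

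**Power at 60 enrolments (noncentral chi-square; simulation in brackets where it differs).**

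| True pattern | 3 df at 0.05 | One factor at 0.025 |
|---|---|---|
| One factor doubles enrolment | 57% (58%) | 64% (65%) |
| Only the combined message doubles it | 61% (58%) | 25% (24%) |
| Both factors double it | 90% (89%) | 64% (65%) |

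**The case against.** **The endpoint and the analysis agree.** Section 3 defines enrolment by message type and 9.4.2 compares it by message type. This stands: Aim 2 as worded in section 3 does have a matching analysis. The mismatch is with the factorial purpose in 4.1 and 4.2.

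**The two effects are written down in advance.** This also stands. A reader might infer that the plan never identifies the trust and endorsement effects, but 4.1 names both factors and their levels as the effects under test. What is missing is the analysis, estimate and interval in section 9. Message type in 9.4.2 might even be meant factor by factor. The text does not say so, and the same rewording would settle it.

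**It is a feasibility study.** With no formal hypotheses and mostly descriptive reporting, error-rate arguments carry little weight. That lowers the severity but does not close the gap: a test is planned on a primary endpoint, and an estimation-minded study has more use for an interval per component than for an omnibus p-value.

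**Power.** A reader might infer that the four-group test is simply underpowered by comparison. The figures do not bear this out. At 0.025 per factor the gain is small when one factor works, and the order reverses when only the combined message works. When both factors work, 3 df again exceeds the power for either single factor, although the chance that at least one of the two is significant at 0.025 is about 87%, close to the 89% simulated for 3 df.

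**Conclusion.** The concern holds as a mismatch between a factorial design and a non-factorial analysis. It is a cheap improvement. It would be too strong to say that the planned test invalidates a result: 9.1 disclaims formal hypotheses, so no confirmatory claim is at risk.

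The central result is that three different messages about the components share one p-value (0.080) on the four-group test, while the factor margins separate trust from endorsement and the interaction ratio separates the third table. This rests on reading 9.4.2 as a four-group test, which is natural but unstated. The figures also rest on 1000 addresses per message and 60 postcard enrolments, neither of which the documents state for the substudy. With fewer postcard enrolments the argument about attribution is unchanged, but the estimates are less precise and their planning value is more modest.

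**What to change.** In 9.4.2, state the primary Aim 2 analysis as the main effects of trust (yes vs no) and endorsement (yes vs no) on enrolment among mailed addressees whose postcards were not returned. Stratify each by the other factor (Mantel-Haenszel). Report risk differences and risk ratios with 95% CIs, presented as estimation in line with 9.1. Report the interaction ratio with its CI and describe it as imprecise.

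Keep the four-cell table and the 3-df chi-square, explicitly labelled as supporting. The table is needed because main effects alone would miss a pattern such as 10/20/20/10. The label matters: a 3-df test at 0.05 counted alongside two factor tests at 0.025 would give about 7% overall error (simulated). This point calls for no change to the website-visit analysis in 9.4.3.

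The cost is wording only, with no new data and no more postcards. The downside is that a main effect averages over the other factor and is less sensitive than the 3-df test if only the combined message works.
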